## 7.22 Safety Analyses

All Safety analyses will be performed using the Safety Population.

Tables will be presented by dose levels. All subjects who received placebo in each of the cohorts will be combined and presented along with the other dose levels.

Unscheduled visits data for all safety variables (vitals, ECG and clinical laboratory) will be listed only and will not be summarized.

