3.2. Study Outcome Measures

3.2.1. Primary Endpoints

- The occurrence of Serious Adverse Events following administration of G03-52-01 to the final follow-up visit.
- The occurrence of Adverse Events from administration of G03-52-01 to the final follow-up visit.
- The occurrence of changes from baseline in physical examination, vital signs and clinical safety laboratory values following administration of G03-52-01 to the final follow-up visit.

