7.15. Unscheduled Visit

A subject may return to the clinic for an unscheduled visit at any time. The following activities at a minimum should be performed:

- Obtain vital signs
- Perform symptom directed PE as appropriate
- Review and update concomitant medications
- Assessment of AEs and SAEs
- Assessment of COVID-19 vaccination status.

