10.3.3.2. Additional Safety Analyses

Vital signs, physical examinations, and clinical laboratory values, including change from baseline, will be summarized by dose cohort and control group.

Descriptive summary statistics for laboratory data at admission (baseline value) and each applicable post-injection visit, including change from the baseline value, will be calculated. Descriptive summary statistics for vital signs at screening (baseline value) and each applicable post-injection visit, including change from the baseline value, will be calculated. Shift tables, showing individual subject changes from baseline will be presented for laboratory parameters using toxicity grading (Appendix B). Subjects with Graded values of vital sign and laboratory parameters will be identified in listings.

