#### 2.2.1 Primary Endpoints

- The occurrence of Serious Adverse Events (SAE) following administration of G03-52-01 to the final follow-up visit.
- The occurrence of Adverse Events (AE) from administration of G03-52-01 to the final follow-up visit.
- The occurrence of changes from baseline in physical examination, vital signs and clinical safety laboratory values following administration of G03-52-01 to the final follow-up visit.

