## 7.22.2 Clinical Laboratory Assessments

Safety Population will be used to present summaries and listings. Clinical laboratory data will be listed and summarized using System International (SI) units.

Laboratory data will be listed by subject at each time point. Clinical laboratory values that are out of normal ranges will be presented in a separate listing.

Observed and change from baseline of continuous clinical laboratory values (serum chemistry, coagulation panel, hematology, and urinalysis) for each parameter will be summarized by dose cohort and control group at each scheduled nominal time point. Categorical Urinalysis will be presented in the listing.

The number and percentage of subjects with shift from baseline based on the laboratory normal ranges will be tabulated.

For female subjects, urine/ serum pregnancy test results will be presented in the individual subject data listings for each visit.

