### **7.22.3 Vital Signs**

Vital signs data will be listed by subject at each nominal time point. Observed and change from baseline vital signs values will be summarized by dose cohort and control group at each nominal timepoint.

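### The SAP leaves unscheduled vital-sign and laboratory values out of every counted summary, so the any-time primary endpoint of change from baseline can be under-counted

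*SAP*

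**What the plan says.** The third primary endpoint, in Protocol 3.2.1 and SAP 2.2.1, is "The occurrence of changes from baseline in physical examination, vital signs and clinical safety laboratory values following administration of G03-52-01 to the final follow-up visit".

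SAP 7.22 sets a general rule for the safety tables: "Unscheduled visits data for all safety variables (vitals, ECG and clinical laboratory) will be listed only and will not be summarized".

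The sections below it work by visit. In SAP 7.22.2, observed laboratory values and changes "will be summarized by dose cohort and control group at each scheduled nominal time point". For shifts, the same section says: "The number and percentage of subjects with shift from baseline based on the laboratory normal ranges will be tabulated". SAP 7.22.3 says: "Observed and change from baseline vital signs values will be summarized by dose cohort and control group at each nominal timepoint".

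Protocol 7.15 allows for off-schedule contact: "A subject may return to the clinic for an unscheduled visit at any time". Its minimum content for such a visit includes vital signs but no laboratory test.

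Protocol 10.3.3.2 asks for laboratory shift tables by Appendix B toxicity grade. It places graded vital-sign and laboratory values in listings. It does not exclude unscheduled values from any summary.

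**The concern.** The endpoint asks whether a change occurred in a subject between dosing and the final visit. The planned tables answer a narrower question: what was seen at the scheduled visits. Where the two differ, the difference runs one way, because dropping post-dose values can only lower the number of subjects counted as having a change.

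The experience cited in Protocol 2.3.1 makes this more than formal. Every related adverse event listed after the similar product NTM-1631 was a laboratory finding, and one was a raised AST two months after infusion. In the present trial the Day 60 visit has no safety blood draw, so a passing change at that time could be seen only in an unscheduled sample. At stake is how completely a primary safety endpoint is reported by dose against pooled placebo.

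**Working it through.** The plan states no figure for this point, so there is none to reproduce. The check compares the endpoint with the planned outputs and then works out the gaps in the schedule.

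**1. Which outputs can count an off-schedule value?** (SAP 7.22 to 7.22.3 and SAP Section 8)

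| Output | Content | Unscheduled values |
|---|---|---|
| Table 14.3.5.1 | Laboratory values and changes, by scheduled time point | Excluded |
| Table 14.3.5.2 | Subjects with a laboratory shift, by normal range | Excluded; SAP 7.22 makes no exception |
| Table 14.3.5.3 | Vital signs and changes, by nominal time point; no subject count | Excluded |
| Table 14.3.4.1; Listings 16.2.8.2, 16.2.8.3, 16.2.8.6 | Individual values, no counts | Kept (Table 14.3.4.1 and Listing 16.2.8.3: abnormal laboratory values only) |
| Tables 14.3.1.1 to 14.3.1.4 | Treatment-emergent adverse events by subject | Only if reported as an adverse event |

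The SAP does not say whether the laboratory shift is by visit or to the worst value. Under either reading an unscheduled value is left out: a by-visit table has no place for it, and a worst-value table would fall under SAP 7.22. Vital signs have no shift table, so the occurrence of a vital-sign change is not counted even from scheduled data. The rule in SAP 7.22 does not name physical examination, so this point covers only the laboratory and vital-sign parts of the endpoint.

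**2. How long are the gaps between scheduled measurements?**

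- Post-dose safety blood draws (Protocol 7.7 to 7.9, 7.13, 7.14 and Table 2): Days 8, 15, 30 and 120 in Cohorts 1-3; Days 8, 15, 30 and 180 in Cohort 4.
- Longest gap, Cohorts 1-3: 120 − 30 = 90 days, and 90/120 = 75% of follow-up.
- Longest gap, Cohort 4: 180 − 30 = 150 days, and 150/180 = 83%.
- Vital signs are taken at every scheduled visit. Longest gap, Cohorts 1-3: 90 − 60 = 30 days (and again 120 − 90 = 30). Cohort 4: 180 − 120 = 60 days.

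**3. What does one subject weigh?** Each cohort has 8 active subjects (Protocol Table 1): 1/8 = 12.5 percentage points. Pooled placebo is 4 × 2 = 8 subjects, so the weight there is the same.

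**4. How many subjects would be affected?** The documents give no rate of unscheduled visits or tests, so this cannot be computed. If k of 8 subjects in a column had an abnormality only off schedule, the count would be short by k/8. Assuming k = 0, 1 or 2, that is 0, 12.5 or 25 percentage points. These values show the scale and are not a forecast.

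**The case against.** **The values are still reported.** This stands. Abnormal laboratory values appear by subject in Table 14.3.4.1 and Listing 16.2.8.3, and vital signs in Listing 16.2.8.6. Listings do not, however, give an incidence by dose against pooled placebo.

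**The adverse-event tables are a safeguard.** This stands in part. Protocol 8.1 counts abnormal laboratory findings among possible adverse events, Appendix B grades both laboratory values and vital signs, and SAP 7.22.1 counts events by maximum severity whatever the visit. The NTM-1631 laboratory findings were themselves captured as adverse events. But the route depends on investigator reporting. The SAP's own definition (3.15) leaves out the laboratory wording, and only new or worsening physical examination findings are expressly required to be reported. The endpoint list also keeps changes from baseline separate from adverse events.

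**The laboratory gap is a feature of the schedule.** This stands. The 75% and 83% describe time without a scheduled safety blood draw. Since no laboratory test is in the minimum set for an unscheduled visit, nothing shows that values will exist in those gaps. Vital signs are in that set, but their scheduled gaps are much shorter.

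**The consequence is limited.** This also stands in part. The trial is descriptive, with 40 subjects and no hypothesis test. The protocol itself puts graded values in listings.

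**Conclusion.** The point holds as a reporting gap. Under SAP 7.22 no counted laboratory or vital-sign summary can contain an unscheduled value, and no worst-post-baseline table exists, although the primary endpoint runs over the whole follow-up. The direction is towards under-counting. The size is unknown: one affected subject is worth 12.5 percentage points of a dose column.

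A reader might infer more, and the documents do not support it:

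- That abnormal values disappear from the report. They remain in listings, and those reported as adverse events are counted.
- That 75% or 83% of laboratory changes would be missed. Those figures measure the window between blood draws.
- That off-schedule values are mostly symptom-driven and so mostly abnormal. This is plausible, but Protocol 7.15 says nothing on why subjects return.
- That dose escalation is compromised. Protocol 8.5.3 has the safety committee review all available safety data, so SAP 7.22 does not touch it.
- That early-termination and repeat values are excluded too. Early termination is a named visit, and the SAP does not say how repeats at a scheduled visit are classed. Their handling is unclear and should be stated.

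**What to change.** Keep the by-visit summaries on scheduled data. Amend SAP 7.22, 7.22.2 and 7.22.3 to add:

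- for laboratory parameters, a shift table from baseline grade to worst post-baseline grade;
- for vital signs, a matching count of subjects by worst post-baseline grade;
- a statement that both use all post-dose values, including unscheduled, early-termination and repeat values.

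Use the Appendix B grades. The normal ranges behind Table 14.3.5.2 carry no order of severity, so a worst value cannot be graded from them. Protocol 10.3.3.2 already requires toxicity-grade shifts for laboratory parameters, so the change also brings the SAP into line with the protocol. Parameters that Appendix B does not grade, such as direct bilirubin, can stay on normal ranges.

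The cost is SAP wording, two tables, and one derived record per subject and parameter; no extra data are collected. The small downside is that subjects with more visits have more chances of an abnormal value. The scheduled-only tables, kept alongside, make that visible.

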### 7.22.1 Adverse Events

All AEs will be classified by Primary System Organ Class (SOC) and Preferred Term (PT) according to the MedDRA, Version 23 or later. Only treatment-emergent AEs (TEAEs) will be included, ie, AEs that begin or worsen after dose of study drug has been received.

The following AE summaries will be presented (where applicable the number of patients (%) and number of events will be summarized) by dose cohort and control group:

- Overall summary of TEAEs
- TEAEs by SOC and PT
- TEAEs by maximum severity
- TEAEs by closest relationship

The overall incidence of TEAEs (number and percentage of subjects) as well as the number of events will be summarized by study drug; severity of TEAE; SAE; relation to study drug of TEAE and SAE; TEAEs leading to study or study drug discontinuation; and TEAEs leading to death will be tabulated for each study drug.

Study drug related AEs are those which were determined by the investigator to be study drug-related. The incidence of study drug related AEs (as recorded in the CRF) will be summarized using descriptive statistics by SOC and PT, categorized by severity and relationship to study

drug as recorded in CRF. The frequency of treatment emergent AEs (AE burden) will be summarized using descriptive statistics by SOC and PT.

For the incidence at the subject level by SOC and PT, if a subject experience more than 1 event within the same SOC and PT, only 1 occurrence will be included in the incidence. Although all the occurrences will be included in the counting of events.

For the incidence at the subject level by SOC, PT, and severity, if a subject experience more than 1 event within the same SOC and PT, only the most severe occurrence will be included in the incidence. Although all the occurrences will be included in the counting of events.

For the incidence at the subject level by SOC, PT, and relationship to study drug; if a subject experience more than 1 event within the same SOC and PT, only the most closely related occurrence will be included in the incidence. Although all the occurrences will be included in the counting of events.

Relative day of AE onset = AE onset date – date of dosing of study product + 1

Treatment Related AEs are those AEs which can be categorized under the relation “POSSIBLY RELATED” and/or “DEFINITELY RELATED”.

All AE data will be listed for all patients. Both the Investigator's verbatim terms and the MedDRA preferred terms will be listed for each patient. AEs listings will also include start and end date, relationship to study drug, severity, action taken for the AEs and if the AE is serious.

Any SAEs, AEs with outcome of death, or AEs resulting in discontinuation of study or study drug will be listed separately.

AEs recorded as Reactogenicity will be listed by each subject and summarized by dose level and control group similarly as described above. Summaries will be provided for severity and closest relationship.

## 7.22.2 Clinical Laboratory Assessments

Safety Population will be used to present summaries and listings. Clinical laboratory data will be listed and summarized using System International (SI) units.

Laboratory data will be listed by subject at each time point. Clinical laboratory values that are out of normal ranges will be presented in a separate listing.

Observed and change from baseline of continuous clinical laboratory values (serum chemistry, coagulation panel, hematology, and urinalysis) for each parameter will be summarized by dose cohort and control group at each scheduled nominal time point. Categorical Urinalysis will be presented in the listing.

The number and percentage of subjects with shift from baseline based on the laboratory normal ranges will be tabulated.

For female subjects, urine/ serum pregnancy test results will be presented in the individual subject data listings for each visit.

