## 1. INTRODUCTION

This statistical analysis plan (SAP) is consistent with the statistical methods section of the final study protocol (Version 3.0, dated 07 Sept 2021) and includes additional detail of pharmacokinetic (PK), immunogenicity, safety and tolerability summaries to be included in the clinical study report (CSR).

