**Section 14.3.5      Additional Safety Data Summaries**

Table 14.3.5.1      Absolute and Change from Baseline of Clinical Laboratory Results by Category and Test (Safety Population)

Note: please include only continuous tests

Table 14.3.5.2      Shift from Baseline in Clinical Laboratory Results (Safety Population)

Table 14.3.5.3      Absolute and Change from Baseline for Vital Signs (Safety Population)

Table 14.3.5.4      Shift from Baseline in Physical Examination (Safety Population)

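### SAP 7.22.2 tabulates laboratory shifts by normal range where Protocol 10.3.3.2 requires Appendix B toxicity grades, and the SAP declares no departure

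*SAP*

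**What the plan says.** Protocol 10.3.3.2 makes two commitments on graded safety data. One concerns tables: "Shift tables, showing individual subject changes from baseline will be presented for laboratory parameters using toxicity grading (Appendix B"). The other concerns listings: "Subjects with Graded values of vital sign and laboratory parameters will be identified in listings".

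SAP 7.22.2 uses a different basis for the table: "The number and percentage of subjects with shift from baseline based on the laboratory normal ranges will be tabulated". The output list in SAP 8 has one laboratory shift table, Table 14.3.5.2, titled "Shift from Baseline in Clinical Laboratory Results (Safety Population"), and no graded one. For dipstick results the SAP says "Categorical Urinalysis will be presented in the listing". The separate abnormal-value listing is defined by normal range. For vital signs, SAP 7.22.3 says "Vital signs data will be listed by subject at each nominal time point" and names no grade.

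SAP 1 nevertheless says: "This statistical analysis plan (SAP) is consistent with the statistical methods section of the final study protocol". SAP 4 says the same of every analysis it specifies and records no departure.

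On baseline, SAP 7.1 gives one rule for all variables: the latest measurement before the dose date. Protocol 10.3.3.2 gives two: admission for laboratory data and screening for vital signs.

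**The concern.** Change from baseline in safety laboratory values is part of a primary endpoint (Protocol 3.2.1, SAP 2.2.1) in a first-in-human dose-escalation study with eight active subjects per dose. The halting and escalation criteria in Protocol 8.5.1 and 8.5.2 are written in grades. A table with only low, normal and high categories cannot be read against them. It puts Grades 1, 2 and 3 in one category, and it shows no change for a subject who worsens from a Grade 1 baseline.

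The protocol's grade-by-grade view by dose would not be produced. Because SAP 1 and 4 state consistency, a reader would not learn that it had been replaced.

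**Working it through.** The plan states no figure on this point, so there is none to reproduce. The check compares the two texts and then classifies values both ways using Appendix B.

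**1. The texts side by side**

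| Item | Protocol 10.3.3.2 | SAP |
|---|---|---|
| Laboratory shift table | Appendix B grade | Normal range (7.22.2, Table 14.3.5.2) |
| Laboratory listings | Graded values identified | All values, and values out of range; no grade mentioned |
| Vital-sign listing | Graded values identified | Values by time point; no grade mentioned |
| Urine protein, glucose, blood | Graded in Appendix B | Categorical results listed only |

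The first row is a conflict between stated rules. The listing rows are omissions, since a listing could still carry a grade.

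**2. How many tests are affected**

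The test list comes from Protocol 6.5.2, leaving out the red-cell and platelet indices stated to be ungraded. WBC with differential is counted as WBC plus the five cell types in Appendix B.

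- Haematology: 8 of 8 graded. WBC is graded in both directions. Haemoglobin, neutrophils, lymphocytes and platelets are graded for decreases only (4). Monocytes, eosinophils and basophils are graded for increases only (3).
- Chemistry and coagulation: 13 of 15 graded. Sodium, potassium and calcium are graded in both directions (3). Creatinine, BUN, total bilirubin, alkaline phosphatase, PT, PTT, INR, ALT, AST and CK are graded for increases only (10). Direct bilirubin is marked NA and indirect bilirubin is not listed.
- Graded: 8 + 13 = 21 of 8 + 15 = 23.
- Both directions: 1 + 3 = 4. One direction: 4 + 3 + 10 = 17.

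**3. What the normal-range table hides**

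- ALT, men: normal <41, Grade 1 is 41–100, Grade 3 is >200 U/L. From a normal baseline, 42 and 250 U/L both appear as normal to high, each counting as 1/8 = 12.5% of a dose group.
- CK: normal 39–308, Grade 1 is 309–1000, Grade 3 is >1500 U/L. Protocol 4.1.1 allows a screening CK below 400 U/L. A rise from 350 to 1600 U/L is 1600 − 350 = +1250, Grade 1 to Grade 3, yet it is recorded as high to high. The high category runs from 309 to beyond 1500 U/L, and 1500/308 = 4.9 times the upper limit.
- Platelets of 149, 119 and 99 (10³/mm³) are all low, but are Grades 1, 2 and 3.

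**4. Where the two classifications disagree**

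- Appendix B has separate WBC and neutrophil limits for African American subjects. In African American men, WBC 9,500 is normal by range (4,000–10,000) but Grade 1 (9,001–14,000), so it would also be missing from the out-of-range listing. WBC 3,000 and neutrophils 1,500 are low by range but ungraded.
- Neutrophils 9,000 (normal 1,700–7,000) or platelets 500 (normal 150–400) are high by range but have no grade. Protocol 2.3.1 reports a related neutrophil increase with a similar product, so the normal-range table has its own use.

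**5. Baseline (secondary)**

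If SAP 7.1 means the dose date literally, the Day 0 laboratory sample is excluded, although Protocol 10.3.3.2 calls admission the baseline. If it means dose time, the pre-injection vital signs (SAP Table 3-2, note 4) become baseline, against Protocol 6.3, Protocol 10.3.3.2 and SAP 3.17. Neither reading meets both protocol rules. The two readings place laboratory baseline on Day 0 or at a screening sample 3 to 28 days earlier. Protocol 6.5.2 and SAP 3.16 add to the doubt by placing the tests at screening and end of study and by treating a Grade 1 value as baseline.

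**The case against.** The strongest reply is that little is lost from sight. SAP 7.1 requires the minimum, maximum and quartiles, so an ALT of 250 U/L at a scheduled visit would be the maximum in Table 14.3.5.1 or be exceeded by it. Out-of-range values are listed individually. Appendix B heads its laboratory section as adverse events, Protocol 8.1 counts abnormal laboratory findings as possible adverse events, and Protocol 8.5.1 speaks of Grade 3 events in laboratory tests. A Grade 3 value would therefore probably reach Table 14.3.1.3. SAP 7.1 lists everything in the database, so a stored grade would appear, and SAP 4 sends later changes to the study report.

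Much of this stands as mitigation. It does not replace the table. No passage requires every graded value to be reported as an adverse event, or says that a grade is captured or derived for laboratory or vital-sign values. Group summaries do not show individual movements between grades, and SAP 7.22 keeps unscheduled values out of all summaries. The provision for later changes does not cover a difference already present when SAP 4 was written.

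The test count can also be challenged. The Protocol Summary mentions a comprehensive metabolic panel, and Appendix B also grades glucose (both directions), albumin, total protein, haematocrit and red cells. If these are measured, the totals rise. The conclusion does not change.

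On baseline, SAP 3.17 settles vital signs, and Protocol 7.2 schedules safety laboratory tests before dosing on Day 0. The remaining doubt is mainly one of wording.

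**Conclusion.** The concern holds. On laboratory shifts the SAP states a rule that conflicts with the protocol and does not declare it. The missing grades in the laboratory and vital-sign listings are an omission. For 21 of the 23 blood tests in Protocol 6.5.2, the planned table cannot distinguish Grades 1, 2 and 3. Grade by dose is then tabulated only for values reported as adverse events.

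The point should be fixed, but its reach is limited. It changes no sample size or error rate. Escalation rests on Safety Review Committee review of Day 8 data (Protocol 8.5.3, 8.6.4), not on this table. The counts assume the Protocol 6.5.2 test list and a five-part differential. The baseline ambiguity is a lesser point.

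**What to change.** **Table.** In SAP 7.22.2 and SAP 8, add a shift table of baseline grade (0–3) by post-baseline grade (0–3) per Appendix B, by dose level and pooled placebo.

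- State which post-baseline value is used, for example worst grade or by visit, and whether unscheduled values count. Protocol 10.3.3.2 does not say.
- Split by direction every measured test graded both ways: sodium, potassium, calcium and WBC, plus glucose if it is run.
- Apply the separate WBC and neutrophil limits where Appendix B gives them.
- Include urine protein, glucose and blood. Microscopy follows only an abnormal dipstick, so give a rule for subjects without it.
- Grade results in Appendix B units before conversion, because SAP 7.22.2 says "Clinical laboratory data will be listed and summarized using System International (SI) units".
- Keep Table 14.3.5.2, since 17 of the 21 graded tests are graded in one direction only.

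**Listings.** Add an Appendix B grade column to Listings 16.2.8.2, 16.2.8.3 and 16.2.8.6.

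**Alternative.** If only the normal-range table is intended, declare and justify the departure in SAP 4 and correct SAP 1.

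**Baseline.** In SAP 7.1, state separate rules: for laboratory tests, the last non-missing value before injection, including Day 0; for vital signs, the screening value as in SAP 3.17. Align SAP 3.16, and clarify Protocol 6.5.2 against Protocol 10.3.3.2.

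**Cost.** One table, a grade column in three listings, one or two SAP sentences and a short protocol clarification. No new data are needed and no planned output is removed.
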